The **primary objective** of this sub-study is to investigate the cortical and non-cortical changes induced by CN-NINM training in patients with symptoms due to a mild to moderate TBI. In this sub-study, we will use functional magnetic resonance imaging (fMRI) tasks to identify the anatomical locations of the modulated neural activity induced by the tongue stimulation and how these changes can produce the behavioral and subjective improvements seen in patients with balance disorders after therapy with CN-NINM. A **secondary objective** is to evaluate the relationship between changes in brain and behavioral measures over time. We will evaluate the **hypothesis** that CN-NINM induces greater neuroplasticity in the Active than the Control group in areas involved in balance processing as well as by evaluation of major cranial nerves involving the tongue: trigeminal, CN-V, and facial, CN-VII and CN XII. An optic flow fMRI task will be used to evaluate areas involved in balance processing. A jaw-clenching fMRI task will be used to evaluate CN-V; A Tongue-thrust fMRI task will be used to evaluate CNV, VII, and CN-XII. This stimulation also has a cascading effect on neural activity in the brainstem (pons varolli and medulla), and cerebellum and higher order cortical structures such as the anterior cingulate. Neuroplasticity changes will be measured by task fMRI activation changes.

In addition to traditional task fMRI we will also use **advanced neuroimaging methods** to characterize functional and structural brain connectivity patterns in this population. **Resting state fcMRI** (rs-fcMRI) refers to the temporal coherence between different brain regions indicated by spontaneous blood-oxygen-level dependent fluctuations in the absence of any active task performance, i.e., when the brain is “at rest” [1-3]. Strong coherence has been identified between clinically relevant networks such as the somatomotor, visual, language, memory, and other functional networks and several studies have demonstrated test-retest reliability of rs-fcMRI measures. In a group of TBI patients in the sub-acute to chronic stage, Bonelle and colleagues recently showed that abnormality in default mode network (DMN) function is a sensitive marker of impairment of sustained attention [4].

To identify abnormal structural connectivity patterns in the concussed brain we will collect Diffusion Tensor Imaging (**DTI**) data. DTI evaluates integrity of the white matter (WM) by exploiting the fact that water diffuses faster along the main axis (λ_1) of fibers compared with diffusion perpendicular to fibers (λ_2 and λ_3) [5-8]. Neuroplasticity changes over time from pre- to post-stimulation will be measured by functional connectivity as measured by rs-fcMRI and diffusivity and tractography measures as measured by DTI.

Methods

Sub-study Inclusion and Exclusion Criteria.

In addition to the inclusion and exclusion criteria in the main study, we will also exclude any subjects with contraindications to MR (e.g., claustrophobia, metal implants, etc.).

Subjects must also complete the MRI Screening Form (UWH# SR301436-DT [Rev. 02/17/14]) to determine final MRI Sub-study eligibility. The MRI Screening Form will be reviewed with subjects prior to each scanning session for any changes that could affect eligibility.

Total Subjects.

The sub-study will enroll 26 subjects (13 subjects in the Active PoNS™ group; 13 subjects in the Control group).

Consent Process.

After completion of the TBI Study consent, the Study Coordinator will also provide informed consent for the MRI Sub-study and explain that participation in the sub-study is optional. All candidates will be informed that declining participation in the MRI Sub-study will not affect their participation in the TBI Study. The PIs for both studies will be available to answer candidates' questions. All candidates are free to decline participation in either study without question if they so choose. Subjects will be given a copy of the signed consent form(s).

Compensation for Participation.

Subjects are eligible for the main TBI Study compensation; there is no additional compensation for completion of the MRI Sub-study.

[figure not shown]
Data Points

The imaging scans performed in this sub-study will coincide with the 4 major data collection points in the main study (Table 1): (1) at baseline (after enrollment but before training has begun); (2) at the end of the 2-week in-lab training period; (3) at the end of the 12-week at-home training period; and (4) at the end of the 12-week withdrawal period. For data consistency, every attempt will be made to schedule MRIs on the exact dates listed in Table 1 or within 2 business days after that date. If any anomalies or unforeseen circumstances occur (e.g., inability to schedule MRI scans due to scheduling conflicts, etc.) MRIs may be performed at the next closest in-lab training session or scheduled test point. The decision to perform MRIs outside of the visit schedule listed in Table 1 will be made on a case-by-case basis at the discretion of the PI.

Table 1 – Event timeline for each subject in the study

	Initial Visit	Stage 1 (2 weeks)	Stage 2 (12 weeks)	Stage 3 (12 weeks)
	Prior to beginning intervention	Last day of 2nd week	Last day of 12th week	Last day of 12th week
Informed Consent	X			
fMRI Sub-study	X	X	X	X
Adverse events		X	X	X

Sample size consideration: Power calculation is based on 2-sample t-test using the standard G*Power 3.1.9.2 package [9, 10]. With $n = 13$ patients in the Active PoNS group, and $n=13$ in the healthy control group, at a two-sided significance level of 0.05, we will have 85% power for detecting an effect size of 1.2 standard deviations (see figure below) in our primary outcome

measure of signal change in task fMRI. Our data from our preliminary study with $N=12$ subjects was sufficiently powered to detect a significant effect of the intervention on brain changes as assessed by similar task fMRI [11] as proposed in this study.

Functional MRI

Scanning and Analysis

All MRI data will be acquired with the University of Wisconsin-Madison Department of Radiology's 3T MRI scanner (GE Healthcare, Waukesha, WI) using an 8-channel brain coil. The T1-weighted anatomical scans will be acquired with a 3D-SPGR pulse sequence ($TR = 10$ ms, $TE = 3$ ms, 94 slices, $0.938 \times 0.938 \times 1.5$ mm resolution). One functional scan will be acquired with a T2*-weighted gradient-echo echo-planer imaging sequence (time repetition = 2000 ms, acquisition time = 1800 ms, echo time = 30 ms, flip angle = 75 degrees) to acquire BOLD signal in a 128×128 matrix over a 12cm^2 FOV and 10 slices giving a resolution of $0.938 \times 0.938 \times 2.0$ mm³ centered over the brainstem and cerebellum. This increase in resolution will allow for multiple measurements of BOLD signal in each brainstem nuclei, which are on the order of $3 \times 3 \times 3$ mm³, smaller than a single voxel at standard fMRI resolutions [12]. A second functional scan will be acquired with a T2*-weighted gradient-echo echo-planer imaging sequence (time repetition = 2000 ms, acquisition time = 1800 ms, echo time = 30 ms, flip angle = 75 degrees) to acquire BOLD signal over 30 axial slices ($3.75 \times 3.75 \times 4.5$ mm resolution) covering the entire brain.

Rs-fcMRI data: A 10 minutes eyes closed, whole brain resting state scan will be collected using gradient-echo echo-planer imaging with the following parameters: $TR = 2.6$ s, $TE = 22$ mms, field of view = 22.4 cm, flip angle = 60°, 40 sagittal slices, acquisition matrix = 64×64 , 3.5 mm isotropic voxel size, 162 time-points. T1-weighted anatomical images will be collected for overlaying the fMRI data using a FSPGR BRAVO sequence ($TR = 8.132$ ms, $TE = 3.18$ ms, $TI = 450$ ms) over a 256×256 matrix and 156 slices (flip angle = 12°, FOV = 25.6 cm, slice thickness = 1 mm).

Resting data will be preprocessed as in our earlier studies [13] using FSL and AFNI [14-16]. Data will be motion and slice-time corrected, spatially smoothed using a Gaussian kernel of 6 mm FWHM, and scaled to the grand mean. Time series will be band-pass filtered (0.005 – 0.08 Hz), linear and quadratic trends removed. To control for participant head motion and physiological noise, motion parameters, white matter and CSF signal will be regressed from the time series. The

residual time series will be demeaned, re-sampled to 3 mm³, registered to MNI152 standard space using FSL's FLIRT program.

Seed-based connectivity analyses: Time courses will be extracted from 160 seed regions of interest (ROIs) previously defined in the literature that were generated from meta-analyses focused on tasks involved in high level cognitive and motor functions [17]. The time series from these spherical seed-regions, each 6 mm radius, will be extracted from the spatially standardized residuals for every EPI scan. The resulting time series for each seed-region per scan per subject will be then imported into Matlab (Mathworks) and correlated against every other seed-region, creating 160x160 roi-to-roi connectivity matrices containing correlation coefficients for each subject. Correlation coefficients will be z-transformed using Fisher's r-to-z transformation to normalize the distribution and will be used as inputs to the NBS [18, 19] toolbox (as in the preliminary study [20]). NBS is a non-parametric approach that controls for family-wise error (FWE) in mass-univariate testing of an N x N ROI-to-ROI connectivity matrix and identifies networks of regions that is significantly different between groups.

DTI data: Diffusion Tensor Imaging (10 minute) scans will be collected using single shot diffusion weighted EPI images, 21 contiguous slices[b=0 sec/mm² and b=1000sec/mm²], with TR=4500 ms, TE=71.8 ms, FOV = 24 x 24 cm, 3mm slice thickness, amplitude of diffusion gradient = 40 mT/ applied in 56 non-collinear directions uniformly distributed in three-dimensional space.

DTI data will be processed using FSL (v5.0) [21] with the following steps: 1) correction for motion and eddy current distortion; 2) head-motion correction for gradient direction vectors; 3) image registration and brain mask extraction; 4) estimation of tensor diffusion and generating diffusivity measures; 5) registration of standard white-matter atlases (JHU-ICBM-FA-2mm.nii.gz and JHU-ICBM-labels-2mm.nii.gz) to each patient's native space; 6) estimation of diffusivity measures for specific tracts of interest.

Task fMRI: 1) In order to evaluate regions involved in balance processing, a checkerboard pattern will be used as the basis for a 2-dimensional visual stimuli in an optic flow task. A static checkerboard of alternating black and white squares will be used (CBstat) as the control stimulus. A rotating checkerboard (CBrot) will also be employed, in which the image appears to cyclically approach and recede relative to the observers' viewpoint, as well as rotate about the center of the viewfield [22]. During the scan, subjects will be shown the visual stimuli using a pseudo-randomized block-design paradigm. Each stimulus will be displayed for twelve seconds in blocks of three to six repetitions. Within a block, the stimulus presentations will be separated by six seconds of fixation to reduce the contamination of neural responses from one stimulus presentation into the next [23]. Each block will be separated by six seconds of fixation. The order of stimulus presentation will be the same for all subjects. Task scan will be approximately 7-8 minutes. **2)** In order to evaluate CNV, subjects will perform a jaw-clenching task, in which subjects will alternate between 20 seconds of jaw-clenching and 20 seconds of rest for a total of 6 cycles or 4 minutes. **3)** In order to evaluate CNV, VII, CNXII, subjects will perform a tongue thrust task in which they will alternate between thrusting their tongue to the roof of the mouth for 20 seconds and 20 seconds of rest for a total of 6 cycles or 4 minutes. We will also evaluate relationship of these brain MRI measures with balance and gait measures for the two treatment groups at each of the four time-points.

Each fMRI sub-study scan will take approximately 60 minutes to complete. All MRI scans will be performed at the Wisconsin Institutes for Medical Research (WIMR), [name].

Statistical Analysis

Task MRI Outcomes: Percent signal change will be computed for specific ROIs based on our previous work [11]. A repeated measures ANOVA will be used with Time (pre-intervention, stage 1, 2 3) as factor to examine change in percent signal over time in the patient group. To assess specific changes due to our intervention, we will perform paired t-tests (pre-intervention & stage 1; pre-intervention & stage 2 etc.). 2-sample t-tests will be used to compare differences between the Active PoNS group and control group.

Resting fcMRI Outcomes: The output from the NBS toolbox is a network of brain regions that are significantly impaired between groups (identified using 2-sample t-test) and networks that are significantly influenced by the intervention over time ((identified using paired t-test) [18, 19]. For each significant network, the toolbox provides a list of all pairwise regions and their connection strengths and the t-statistic associated with each connection.

DTI outcomes: DTI analysis will yield whole brain fractional anisotropy (FA), and diffusivity measures (radial, axial, and mean diffusivity). A repeated measures ANOVA will be used with Time (pre-intervention, stage 1, 2 3) as factor to examine change in FA and diffusivity measures over time. 2-sample t-tests will be used to compare differences in these measures between the Active PoNS group and control group.

Brain Behavior correlations: A Pearson correlation or Spearman rank correlation test, as appropriate, will be used for correlation analyses between brain measures (task fMRI derived percent signal change, resting fcMRI derived connectivity measures, DTI FA and diffusivity measures) and behavioral outcome measures

Potential Risks and Benefits

Functional MRI: MRI, a Class II device, is recognized as a Non-Significant Risk (NSR) device by the FDA. All the systems, features, and accessories that will be used in the scanning of subjects under this protocol will be operating outside the limits identified by the FDA as “Criteria for Significant Risk Investigations.”

Risks

1. MRI: Aside from the standard risks associated with persons with certain metallic implants discussed above, no known risks of MRI exist. We know of no risks or adverse effects from the magnetic fields or radio waves used in the standard MRI pulse sequences. A small increase in risk may be associated with rapid gradient waveform switching times associated with fast MR imaging. In certain situations, the rapid switching of gradient waveforms has caused peripheral nerve stimulation in subjects. Significant nerve stimulation, however, has not occurred as long as the imaging system has been programmed to stay within certain limitations of gradient strength and switching time (dB/dt). The MR scanners currently being used at the UW stay within these guidelines, and any additional pulse sequences which we program in our

laboratory will be designed to stay within the current guidelines for dB/dt established by the FDA.

Occasionally some individuals experience feelings of claustrophobia during an MR exam.

The following instructions will be given to the subjects: Support will be provided to keep you from becoming uncomfortable, and you will be able to stop at any time. Using a microphone built into the MR scanner, a technologist will be able to hear you if you need assistance at any time. Please inform the technologist of any discomfort you may experience during the MR exams.

2. Pregnancy: Women who are pregnant or breastfeeding are excluded from the study. Although there is no evidence that MR exams can cause harm, there may be risks that are not known at this time. For this reason, this sub-study is not approved to enroll pregnant women or those that are breastfeeding.

Adverse Events, Unanticipated Problems

The most likely adverse events are detailed in the “Risks” section above. All unanticipated problems involving risk to subjects or others and all serious adverse events will be promptly reported by the PIs according to proscribed procedure:

<http://my.gradsch.wisc.edu/hrpp/10122.htm>.

Adventitious Findings

The images collected for all subjects will be reviewed for adventitious findings by Co-PI, [name]. Subjects will be informed of all findings of clinical significance. During informed consent, subjects will be provided with the option of whether they will also be informed of findings of uncertain or no known clinical significance and whether any findings should be released to their primary care physician.

References

1. Biswal, B., et al., *Functional connectivity in the motor cortex of resting human brain using echo-planar MRI*. Magn Reson Med, 1995. **34**(4): p. 537-41.
2. Carter, A.R., et al., *Resting interhemispheric functional magnetic resonance imaging connectivity predicts performance after stroke*. Ann Neurol, 2010. **67**(3): p. 365-75.
3. Cordes, D., et al., *Mapping functionally related regions of brain with functional connectivity MR imaging*. AJNR Am J Neuroradiol, 2000. **21**(9): p. 1636-44.
4. Bonnelle, V., et al., *Default Mode Network Connectivity Predicts Sustained Attention Deficits after Traumatic Brain Injury*. The Journal of Neuroscience, 2011. **31**(38): p. 13442-13451.
5. Alexander, A.L., et al., *Diffusion tensor imaging of the brain*. Neurotherapeutics, 2007. **4**(3): p. 316-29.

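### MRI sub-study: the DTI scan as specified covers 63 mm rather than the whole brain, and the 10-minute resting scan as specified lasts 7.0 minutes

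*Protocol*

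**What the plan says.** All of the relevant text is in the protocol's MRI Sub-study addendum. The SAP does not cover imaging.

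- **DTI acquisition** (DTI data paragraph): "Diffusion Tensor Imaging (10 minute) scans will be collected using single shot diffusion weighted EPI images, 21 contiguous slices", with "3mm slice thickness", "TR=4500 ms, TE=71.8 ms" and gradients "applied in 56 non-collinear directions uniformly distributed in three-dimensional space". The number of b=0 volumes, the number of repeats, the slice orientation and the slab position are not given.
- **DTI outcome** (Statistical Analysis, DTI outcomes): "DTI analysis will yield whole brain fractional anisotropy (FA), and diffusivity measures".
- **Whole-brain task scan** (Scanning and Analysis): the second functional scan is planned "to acquire BOLD signal over 30 axial slices", 4.5 mm thick, and is described as covering the entire brain.
- **Resting scan** (Rs-fcMRI data paragraph): "A 10 minutes eyes closed, whole brain resting state scan will be collected", using a TR of 2.6 s, 40 sagittal slices and "3.5 mm isotropic voxel size, 162 time-points".

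The addendum's introduction names resting connectivity, and DTI diffusivity and tractography, as measures of neuroplasticity over time. The sample size paragraph names task-fMRI signal change as the sub-study's primary outcome.

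**The concern.** Slice count times slice thickness gives the depth of tissue imaged, and time-points times TR gives the length of a scan. On the stated entries, the DTI stack is too shallow for the outcome that the analysis section promises, and the resting scan is shorter than its label. No other paragraph reconciles either pair.

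This is more than a matter of wording. Staff who program the scanner from this text would acquire DTI data that cannot give a planned outcome, and tissue that was not imaged cannot be recovered afterwards. The sub-study's interest runs from brainstem and cerebellum to cortical structures such as the anterior cingulate, so where a partial slab lies decides what can be measured. Because no slab position is stated, placement could also differ between a subject's four scans, which would add noise to the analysis of change over time.

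**Working it through.** **Inputs**, all from the addendum:
- DTI: 21 contiguous slices, 3 mm thick, TR 4.5 s, 56 directions.
- Entire-brain task scan: 30 axial slices, 4.5 mm thick.
- Resting scan: 40 sagittal slices, 3.5 mm isotropic voxels, 162 time-points, TR 2.6 s, stated length 10 minutes.

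**Check that the settings read sensibly.** The resting voxel size can be reproduced: a 22.4 cm field of view over a 64 matrix gives 224/64 = 3.5 mm, as stated.

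**1. DTI coverage** = slices × thickness, with no gaps because the slices are contiguous.
- DTI: 21 × 3 = 63 mm.
- Entire-brain task scan: 30 × 4.5 = 135 mm, so DTI covers 63/135 = 47% of it.
- Whole-brain resting scan: 40 × 3.5 = 140 mm, so DTI covers 63/140 = 45% of it.
- The two anatomical scans point the same way: 94 × 1.5 = 141 mm and 156 × 1 = 156 mm.

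The DTI orientation is not stated, but the slab is under half of the addendum's own figure in both the axial and the sagittal direction. The 24 × 24 cm field of view is in-plane and adds no depth. Matching the addendum's own extents needs 135/3 = 45 or 140/3 ≈ 47 slices of 3 mm.

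**2. Resting scan length** = time-points × TR.
- 162 × 2.6 s = 421.2 s = 7.02 minutes. The stated 10 minutes is not reproduced.
- Ten minutes at this TR needs 600/2.6 ≈ 231 time-points. The shortfall is 231 − 162 = 69 volumes, about 3 minutes, which is too many to be discarded start-up volumes.
- To fill 10 minutes with 162 time-points, the TR would have to be 600/162 = 3.70 s.

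**3. Does the 10-minute DTI label also fail?** The answer depends on entries that are not given. Assume 1 to 10 b=0 volumes:
- One pass: 57 × 4.5 s = 4.3 minutes, up to 66 × 4.5 s = 5.0 minutes.
- Two passes: 8.6 to 9.9 minutes.

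Two passes fit the label, so it is not shown to be wrong.

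**4. Time needed for full DTI coverage.** Assume the time per slice stays at 4500/21 = 214 ms.
- 45 slices give a TR of 9.64 s, and 57 volumes then take 9.2 minutes in one pass or about 18 minutes in two.
- 47 slices give a TR of 10.07 s, so 9.6 minutes in one pass or about 19 minutes in two.

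**The case against.** The strongest reply is that these may be slips in reporting rather than wrong scanner settings. The DTI paragraph shows signs of careless drafting (the gradient amplitude has lost part of its unit), and the documents cannot show whether the scanner or the text is wrong. That stands as a caution about cause. It does not remove the conflict, because the text is what staff would follow. A deliberate partial slab is also unlikely: where the addendum plans restricted coverage, as in the 10-slice scan over the brainstem and cerebellum, it says so.

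Four stronger readings are tempting, and the documents do not support them.

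- *The DTI duration is wrong too.* The number of repeats is not stated, and two passes fit within 10 minutes.
- *The tract analysis is impossible.* The plan estimates diffusivity for specific tracts of interest, which it does not list. Tracts lying wholly inside the slab can still be measured. What fails is the whole-brain summary and any tract that leaves the slab.
- *Resting connectivity loses 30% of its data, with about 19% more error.* These figures (1 − 421.2/600, and the square root of 231/162) assume that 10 minutes is the intended value. The 162 time-points are equally part of the plan. The 19% also concerns a single within-subject correlation. The planned group tests carry between-subject variance as well, so the loss there is smaller and has not been quantified.
- *The comparison of arms is biased.* The settings are the same for both arms and all four visits.

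It is also fair to say that the stakes are limited. The sub-study is optional, with 26 subjects, and these are additional measures with no power calculation of their own.

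**Conclusion.** Both contradictions hold on the addendum's own figures. DTI as specified covers 63 mm, 45–47% of what the addendum elsewhere treats as the whole brain, so the planned whole-brain fractional anisotropy and diffusivity cannot be obtained from it. The resting scan as specified lasts 7.0 minutes against a stated 10. The first result rests on contiguous slices and a single slab, as written; the second only on the stated TR and number of time-points.

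The consequence is lost or undefined coverage in the DTI measures and an undefined length for the resting scan, and both sets of measures feed the planned brain–behavior correlations. The task-fMRI primary measure of the sub-study, the main trial's SOT endpoint and the comparability of the arms are not affected. The correction should be made because it is cheap before scanning and impossible afterwards for any subject already imaged.

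**What to change.** Before scanning, reconcile the DTI data, DTI outcomes and Rs-fcMRI data paragraphs.

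- **DTI:** take one of two routes. Either correct the slice number and TR so that coverage matches the addendum's own whole-brain extent (about 45–47 contiguous 3 mm slices), or replace the whole-brain claim in DTI outcomes by the region covered and state a fixed slab position. In both cases state the number of b=0 volumes and of repeats.
- **Resting scan:** either set about 231 time-points, or state a length of 7 minutes.
- Use one setting for all subjects and all four visits. If any scans have already been done, record the parameters actually used.

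The cost is a change of wording and of scanner settings. Choosing 231 time-points adds about 3 minutes of scanning, within the time already stated for that scan. Full DTI coverage takes about 9 to 10 minutes in a single pass, but about 18 to 19 minutes if two passes are intended. In that case the total should be checked against the stated session of approximately 60 minutes.

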An independent, optional sub-study, Characterizing Functional and Structural Brain Changes Following Cranial Nerve Noninvasive Neuromodulation (AKA MRI Sub-study), will enroll 26 subjects (13 subjects in the Active PoNS™ group; 13 subjects in the Control group) who are enrolled in the main TBI Study (see [Addendum – MRI Sub-study](#)). MRI scans will be performed at important points during the study: at the beginning and end of the 2-week in-lab CN-NINM intervention period (ITP), at the end of the 12-week home training phase (HTP) and at the end of the 12-week withdrawal phase. This will yield a total of 4 data points for each subject. The sub-study MRI scans will be performed at the Wisconsin Institutes for Medical Research (WIMR), [name].

Methods

Subject Population & Selection.

All subjects will be recruited on a voluntary basis. The study will enroll 44 adults, age 18-65, presenting with a chronic balance deficit due to mTBI. Subjects who also present with other

symptoms, such as gait disturbance, mild to moderate recurrent headaches, sleep, memory, attention, or cognitive deficits, will be considered for participation. All candidates will have had a closed-head, non-penetrating, blunt, whiplash, or explosive blast-induced brain injury. Subjects will be required to provide their most recent neuroradiologic report and evidence of having completed a prescribed therapeutic regimen for their symptoms.

Study Inclusion and Exclusion Criteria.

Inclusion Criteria:

- All candidates will have a balance disorder as a result of a traumatic brain injury (TBI).
- All candidates will have a NeuroCom[®] Sensory Organization Test (SOT) composite score at least 8 points below normal after adjustment for age and height [based on normative data].
- All candidates will be between the ages of 18 and 65 (at the time of screening).
- If female of childbearing potential, the candidate agrees to use adequate contraception throughout participation in the study (from enrollment to completion).
- All candidates must have access to a treadmill.
- All candidates will be at least 1 year post-injury.
- All candidates will have a neuroradiologic scan and report after their most recent TBI.
- All candidates will be ambulatory and able to walk independently for 20 minutes.
- All candidates, if on medications, will not have had any major changes in type or dosage within 3 months of enrollment.

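### The MRI sub-study aims to relate changes in brain and behaviour, but the only timing stated for relating them is visit by visit, and no change-on-change analysis is specified

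*Protocol*

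**What the plan says.** Three places in the protocol's MRI addendum bear on this.

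- **Objectives (opening of the addendum).** The secondary objective "is to evaluate the relationship between changes in brain and behavioral measures over time".
- **Task fMRI paragraph (under Scanning and Analysis).** Its closing sentence says the team will also evaluate the "relationship of these brain MRI measures with balance and gait measures for the two treatment groups at each of the four time-points". This is the only statement of when brain and behaviour are related to each other.
- **Statistical Analysis, Brain Behavior correlations.** "A Pearson correlation or Spearman rank correlation test, as appropriate, will be used for correlation analyses between brain measures" and behavioural outcomes. The brain measures listed are "task fMRI derived percent signal change, resting fcMRI derived connectivity measures, DTI FA and diffusivity measures". The paragraph names no visit or interval, does not choose between levels and changes, and does not say whether the arms are pooled.

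The protocol's Study Design section puts scans at baseline and at the end of each of the three stages: "This will yield a total of 4 data points for each subject". Table 6 of the main protocol schedules SOT, DGI and 6MWT at matching points. The SAP does not cover the sub-study.

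**The concern.** The objective asks whether subjects whose brain measures changed more also improved more. A correlation at one visit asks whether subjects with higher brain values at that visit also have better balance or gait at that visit. These are different quantities.

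Before training starts there is no change to relate, so the baseline correlation says nothing about the objective. Each later correlation combines two sources: differences between subjects that were there before training (injury extent or age, for example) and differences in how much they changed. It can therefore show a relation when the changes are unrelated, or miss one when they are closely related.

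The stake is interpretation. The addendum also wants to explain how neural changes could produce the improvements seen in patients. A same-visit correlation that reflects stable severity could be reported as support for that mechanism. Leaving levels versus changes open also leaves the choice until after the data are seen.

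**Working it through.** **1. The sub-study's own figure.** The addendum gives 85% power for a difference of 1.2 SD with 13 per group at two-sided 0.05. A two-sample t-test with noncentrality 1.2 × √(13/2) = 3.06 and 24 df gives 83.5%; the normal approximation gives 86.4%. The figure reproduces, but it concerns the group comparison of task fMRI signal. No power is stated for the brain-behaviour correlation.

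**2. Does anything else in the plan supply change-on-change?**
- Percent signal change is not a change between visits. The task fMRI analysis uses Time "as factor to examine change in percent signal over time in the patient group", so percent signal is a per-scan value whose change over visits is analysed separately. Connectivity, FA and diffusivity are per-scan values too.
- The repeated-measures ANOVAs and paired t-tests use brain data alone. They show whether the brain measure moved, not whether its movement tracked balance or gait.

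**3. What a same-visit correlation measures.** Assumed model: follow-up = baseline + change for both measures; baseline SD 1; SD of change k; change independent of baseline. With baseline correlation ρ0 and change correlation ρΔ,

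r(follow-up) = (ρ0 + ρΔ·k²) / (1 + k²).

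At baseline, r = ρ0 and ρΔ does not enter.

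**4. A real relation missed.** Take ρ0 = 0 and ρΔ = 0.6.
- k = 0.5: 0.6 × 0.25 / 1.25 = 0.12
- k = 1.0: 0.6 × 1 / 2 = 0.30

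Fisher-z power at two-sided 0.05 is Φ(δ − 1.96) + Φ(−δ − 1.96), with δ = atanh(r) × √(n − 3).

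| Correlation tested | r | n = 26 pooled | n = 13 per arm |
|---|---|---|---|
| Follow-up levels, k = 0.5 | 0.12 | δ = 0.58, 9% | δ = 0.38, 7% |
| Follow-up levels, k = 1.0 | 0.30 | δ = 1.48, 32% | δ = 0.98, 16% |
| Changes | 0.60 | δ = 3.32, 91% | δ = 2.19, 59% |

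**5. An apparent relation when changes are unrelated.** Take ρ0 = 0.5 and ρΔ = 0. Follow-up r = 0.5 / (1 + k²), which is 0.40 at k = 0.5 and 0.25 at k = 1. These would be significant in about 53% and 23% of studies with n = 26 (27% and 13% with n = 13).

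**6. Check by simulation.** With k = 0.7 and 20,000 replicates per case:
- ρ0 = 0.6, ρΔ = 0: follow-up r = 0.6/1.49 = 0.40, significant in 55% (n = 26) or 29% (n = 13).
- ρ0 = 0, ρΔ = 0.6: follow-up r = 0.294/1.49 = 0.20, significant in 16% or 10%, against 92% or 62% for correlating changes.
- ρ0 = −0.3, ρΔ = 0.6: follow-up r = (−0.3 + 0.294)/1.49, about 0. The relation disappears.

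**7. Sensitivity.**
- If change varies more than baseline, the gap narrows. At k = 1.5, r = 0.6 × 2.25/3.25 = 0.42 and power is 56% at n = 26; at k = 2, r = 0.48 and power is 71%. The documents give no baseline SD for SOT or for any brain measure, so k is unknown.
- If 25% are lost, as the main study allows, n is about 20 (26 × 0.75 = 19.5), and 91% falls to about 82%.
- If change scores had reliability 0.5 to 0.7 in both measures (assumed), a true 0.6 would be observed as 0.30 to 0.42, with power 32-57% at n = 26. Levels would be attenuated too, but 91% is a best case.

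**The case against.** The strongest reply is that this is under-specification, not a wrong analysis. The paragraph on brain-behaviour correlations, which sits in the statistical section, is silent on levels versus changes. The visit-by-visit sentence closes an acquisition paragraph, before that section begins, and is worded as an addition. A reader might infer that the plan rules out correlating changes; the documents do not support that. They never specify it, which is a weaker statement.

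Two further inferences also go too far. One is that same-visit correlations are dominated by stable differences: the share is unknown, and at k = 1 the model above splits follow-up variance equally. The other is that this objective is the reason for four scans, so that the repeated data go unused. The primary objective concerns brain changes induced by training, and the ANOVAs and paired tests use all four scans for it.

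It is also fair that the 91% figure rests on pooling and complete data. The phrase about the two treatment groups can be read as within-arm analysis, where the figure is about 59%.

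What stands after this is the mismatch. The objective is about changes, the one stated timing is cross-sectional, and nothing in the addendum or SAP bridges the two.

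**Conclusion.** The concern holds in this limited form: the plan states an objective about change, gives only same-visit timing for addressing it, and specifies no change-on-change or joint longitudinal analysis. That levels and changes are different estimands follows from the algebra and needs no assumed numbers.

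The size does depend on assumptions. The contrast of roughly 9-32% against 91% (7-16% against 59% per arm) requires uncorrelated baselines, change independent of baseline, SD of change no larger than baseline SD, error-free changes and no missing scans. It illustrates the direction of the problem and is not a prediction for this trial.

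Importance is modest. It concerns a secondary objective of an optional 26-subject sub-study and touches neither the main trial's primary endpoint nor safety. It is still worth correcting, because following the stated timing would not answer the stated question.

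**What to change.** Amend the closing sentence of the Task fMRI paragraph and the Brain Behavior correlations paragraph to say:

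- For each post-baseline scan (end of Stages 1, 2 and 3), the change from baseline in the brain measure is related to the change from baseline in composite SOT, DGI and 6MWT over the same interval.
- The analysis adjusts for treatment arm, by partial correlation or regression, so that a mean difference between arms cannot by itself create a pooled correlation.
- Correlations at single time-points are descriptive.
- If lead intervals are named, baseline to Week 2 and baseline to Week 14 match the SAP's primary efficacy endpoint.

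The cost is addendum wording; the scans and tests are already scheduled. Adjusting for arm uses one degree of freedom: at n = 26, δ = 0.693 × √22 = 3.25, so the 91% becomes about 90%. Subjects missing either scan of an interval drop out of that interval.

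The amended text should also acknowledge limited precision. The correlation detectable with 80% power is tanh(2.80/√(n − 3)), about 0.53 with 26 pooled and 0.71 with 13 in one arm, before any missing scans. Estimates should therefore be reported with confidence intervals.
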